2.2 Study Design

This is a randomized, multicenter, open-label, Phase 1b/2 study to evaluate the safety, tolerability, and clinical activity of MEDI4736 in combination with tremelimumab, MEDI4736 monotherapy, and tremelimumab monotherapy in subjects with metastatic or recurrent gastric or GEJ adenocarcinoma who meet the protocol specified criteria.

The dose and schedule of MEDI4736 in combination with tremelimumab for Phase 1b of the current study will be based on emerging safety, clinical, and PK/pharmacodynamics data from the ongoing Study D4190C00006, which is evaluating the combination of MEDI4736 and tremelimumab in subjects with non-small-cell lung cancer (NSCLC). It is anticipated that a dose level and schedule determined as safe in NSCLC will also be safe in subjects with metastatic or recurrent gastric or GEJ adenocarcinoma. Two scenarios are listed in the protocol depending on the dose level and schedule decisions in study D4190C00006.

2.3 Treatment Assignment and Blinding

In Phase 1b, each subject who meets the eligibility criteria will be assigned open-label investigational product.

In Phase 2, subject who meets the eligibility criteria will be enrolled in 1 of 5 treatment arms. Second-line subjects with metastatic or recurrent gastric or GEJ adenocarcinoma will be randomized in a 2:2:1 ratio to Arm A (MEDI4736 in combination with tremelimumab), Arm B (MEDI4736 monotherapy), or Arm C (tremelimumab monotherapy). In parallel, third-line subjects with metastatic or recurrent gastric or GEJ adenocarcinoma will be enrolled in Arm D (MEDI4736 in combination with tremelimumab). As of Amendment 6, second-line and third-line subjects who have a positive IFN- γ gene expression signature as measured in archival formalin-fixed paraffin embedded (FFPE) tumor samples will be enrolled in Arm E (MEDI4736 20 mg/kg in combination with tremelimumab 1mg/kg Q4W). Of the first 20 subjects enrolled into Arm E, no more than 15 subjects may be third-line; no more than 30 subjects may be third-line in the overall cohort.

An interactive voice response system/web response system (IXRS) will be used to assign unblinded investigational product kit numbers. A subject is considered entered into the study when the investigator notifies the IXRS that the subject meets eligibility criteria and the IXRS provides the assignment of unblinded investigational product kit numbers to the subject. For subjects in the randomized portion of the study, the randomization code will be produced by an independent statistician, who is not part of the study team.

2.4 Sample Size

The planned sample size includes up to approximately up to 9 subjects in Phase 1b and up to approximately 126 subjects in Phase 2.

2.4.1 Phase 1b

A safety run-in of up to 9 subjects will be required to investigate the safety and tolerability of the dose level and schedule selected for dose expansion in Study D4190C00006. The sample size for Phase 1b of the study is not based on formal statistical power considerations.

2.4.2 Phase 2

Arms A, B and C (Prior to Protocol Amendment 6)

Approximately 125 subjects will be randomly assigned in a 2:2:1 ratio to Arms A, B, or C. Assuming 10% of the subjects are not evaluable for response or drop-out without a progression free survival (PFS) event before 6 months participation, approximately 45 evaluable subjects for either Arm A or B, and approximately 22 evaluable subjects for Arm C are expected. The sample size determination is based primarily on the consideration of providing the estimation with reasonable precision. As shown in [Table 2.4.2-1](#), when the ORR is expected to be in the 29% to 40% range, a total of 45 subjects would provide a width of 11% to 12% between the observed point estimator and its lower limit of the exact 90% CI. If 24 of 45 subjects have PFS \geq 6 months, the PFS-6 will have an estimate of 53% with a 90% CI of (41%, 65%). Assuming that PFS follows an exponential distribution, the PFS-6 of 53% will correspond to a median PFS of 6.6 months, which is a 50% increase from the 4.4 months observed for ramucirumab plus paclitaxel in subjects with metastatic gastric or GEJ adenocarcinoma following disease progression on first-line platinum- and fluoropyrimidine-based combination therapy in the RAINBOW study ([Wilke et al, 2014](#))

Table 2.4.2-1 Observed ORR and PFS-6 with 90 Percent CI (Arms A and B)

N	Number of Subjects with OR	ORR	2-sided Exact 90% CI	
45	13	29.0%	18%	42%
45	18	40.0%	28%	53%

N	Number of Subjects with PFS at 6 Months	PFS-6	2-sided 90% CI	
45	24	53.0%	41%	65%

OR = objective response; ORR = objective response rate; PFS-6 = progression free survival 6 months

With 45 evaluable subjects for either Arms A or B in Phase 2, the study will have > 90% probability to select the superior regimen if the true difference between the response (or PFS-6) rates in those 2 treatment arms is \geq 14%. In addition, assuming the prevalence of

PD-L1 expression is around 40%, approximately 18 evaluable subjects with high PD-L1 expression for either arms A or B will be expected. The probability of observing at least 1 responder out of 18 evaluable subjects will be at least 90% if the response rate is at least 15%. Additional subjects with high PD-L1 expression may be enrolled in order to further evaluate this population.

With approximately 45 evaluable subjects for Arm A and 22 evaluable subjects for Arm C, the study has 85% power to detect a difference of 35% vs 10% in the response (or PFS-6) rates assuming a 1-sided $\alpha = 0.10$ between the combination arm and the tremelimumab monotherapy arm.

Arm D

It is planned to enroll 25 subjects in Arm D.

Arm E (as of Protocol Amendment 6)

Approximately 40 additional subjects who are biomarker positive will be assigned to Arm E. Assuming 10% of the subjects are not evaluable for response or drop-out without PFS event before 6 months, approximately 36 evaluable subjects for Arm E are expected. The sample size determination is based primarily on the consideration of providing the estimation with reasonable precision. As shown in Table 2.4.2-2, when the ORR is expected to be in the 28% to 39% range, a total of 36 subjects would provide a width of 12% to 14% between the observed point estimator and its lower limit of the exact 90% CI. If 19 of 36 subjects have PFS \geq 6 months, the PFS-6 will have an estimate of 53% with a 90% CI of (39%, 67%). Assuming that PFS follows an exponential distribution, the PFS-6 of 53% will correspond to a median PFS of 6.6 months, which is a 50% increase from the 4.4 months observed for ramucirumab plus paclitaxel in subjects with metastatic gastric or GEJ adenocarcinoma following disease progression on first-line platinum- and fluoropyrimidine-based combination therapy in the RAINBOW study.

Table 2.4.2-2 Observed ORR/PFS-6 with 90% CI (Arm E)

N	Number of Subjects with OR	ORR	2-sided Exact 90% CI	
36	10	28%	16%	43%
36	14	39%	25%	54%

N	Number of Subjects with PFS at 6 Months	PFS6	2-sided 90% CI	
36	19	53%	39%	67%

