3.4.1 Primary Efficacy Endpoints and Analyses

Arms A, B, C and E

The two co-primary efficacy endpoints are Objective response (OR) and PFS-6 based on RECIST v1.1.

Arm D

The primary efficacy endpoint is objective response (OR) based on RECIST v1.1.

The primary efficacy analyses for the primary efficacy endpoint(s) will be based on the As-treated Population.

Objective Response

Objective response (OR) is defined as best overall response (BOR) of confirmed CR or confirmed PR according to RECIST v1.1. The best overall response is defined as the best response (in the order of CR, PR, SD, PD, and not evaluable) among all overall responses recorded from the date of randomization for Phase 2 Arm A, B and C subjects or the date of first dose of study treatment for Phase 1b and Phase 2 Arm D and E subjects until progression, or the last evaluable disease assessment in the absence of PD prior to the initiation of subsequent anticancer therapy or discontinuation from the study, whichever occurs first.

The best overall response (BOR) of CR or PR must be confirmed, which means a response of CR/PR is recorded at 1 visit and confirmed by repeat imaging not less than 28 days (4 weeks) after the visit when the response was first observed with no evidence of progression between the initial and CR/PR confirmation visit. A confirmed CR is defined as two CRs that were

separated by at least 28 days with no evidence of progression in-between. A confirmed PR is defined as two PRs or an un-confirmed PR and an un-confirmed CR that were separated by at least 28 days with no evidence of progression in-between. For a subject to qualify for a BOR of SD, at least 54 days from the randomization date or start of treatment date must elapse without disease progression. The definition of 54 days reflects the protocol-defined disease assessment window of ± 3 days (Day 57 plus/minus 3 days).

Subjects who responded with an unconfirmed CR/PR at the time of data cutoff will be reported as CR/PR pending confirmation under the SD category provided the minimum criteria for SD duration (54 days) are met, otherwise this will be reported under the Non Evaluable (NE) category. NE is assigned for a subject who has only a baseline assessment, or a response assessment of CR/PR/SD at an interval of less than 54 days since randomization or the start of treatment and who has no subsequent disease evaluation, or has all overall response evaluations assessed as NE.

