The ORR is defined as the proportion of subjects with OR. The 2-sided 90% and 95% CI of ORR will be estimated based on the exact probability method. In addition, to help make a comparison to historical data, the unconfirmed ORR which is defined as the proportion of subjects who achieved a best overall response of confirmed/unconfirmed CR or confirmed/unconfirmed PR will be presented along with its CI.

ORR will be compared between the three treatment groups (Arm A, B and C). P-values will be presented without multiplicity adjustment. The comparisons will include the following:

- MEDI4736 + tremelimumab combination therapy (Arm A) versus MEDI4736 monotherapy (Arm B)
- MEDI4736 + tremelimumab combination therapy (Arm A) versus tremelimumab monotherapy (Arm C)

P-values for comparisons of ORR between the treatment groups mentioned above will be obtained from Fisher's exact test. The statistical significant treatment difference will be tested against 2-sided alpha level of 0.05. In addition, the difference in ORR between MEDI4736 + tremelimumab combination and MEDI4736 monotherapy or tremelimumab and associated 95% exact unconditional confidence interval will be provided using Agresti and Ming (2001)'s approach by specifying the RISKDIFF(METHOD=FMSCORE) option in PROC FREQ.

PFS-6

PFS-6 is 6-month progression-free survival rates, which is the proportion of subjects who are progression free and alive at 6 months. PFS is defined as the time from the date of randomization for Phase 2 Arm A, B and C subjects or the date of first dose of study treatment for Phase 1b and Phase 2 Arm D and E subjects to the earlier of the dates of the first objective documentation of radiographic disease progression (per RECIST v1.1) or death due to any cause.

For subjects who are alive with no objective documentation of (radiographic) disease progression by the data cutoff date, PFS will be censored at the date of their last evaluable tumor assessment. If the subject progresses or dies after ≥ 2 consecutively missed or non-evaluable disease assessment visits, PFS will be censored at the time of the latest evaluable disease assessment prior to the missed assessments.

In this study, progression or death after ≥ 2 consecutive missed disease assessment visits is defined (according to disease assessment schedules specified in the protocol) as below:

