- ≥ 18 weeks (two disease assessment visits plus 2 week visit window to allow for a late assessment) since the last post-baseline evaluable disease assessment, if progression or death occurs prior to end of treatment.
- ≥ 26 weeks (three disease assessment visits plus 2 week visit window to allow for a late assessment) since the last post-baseline evaluable disease assessment, if progression or death occurs after end of treatment.

The details of censoring rules are listed in table 3.4.1-1.

Table 3.4.1-1 Summary of Censoring Guidelines for PFS

Situation	Date of PD/Death or Censoring	PFS Outcome
Documented Progressive Disease (PD)	Date of earliest sign of PD	Event
Death prior to second scheduled post-baseline disease assessment or after ≤1 missed or non-evaluable disease assessment following an adequate post-baseline disease assessments	Date of death	Event
No PD or death at time of analysis or lost to follow-up	Date of last adequate progression-free disease assessment	Censored
Death or PD immediately after ≥ 2 consecutive missed or non-evaluable disease assessments	Date of randomization/the first dose of study treatment or last progression-free disease assessment prior to missed or non-evaluable assessments, whichever occurred last	Censored
Initiation of alternative anticancer therapy before PD or death	Date of last adequate progression-free disease assessment prior to initiation of alternative anticancer therapy	Censored
No tumor assessment at baseline and no death prior to second scheduled post-baseline disease assessment, or no tumor assessment post-first dose	Date of randomization/the first dose of study treatment	Censored

Kaplan-Meier curves will be generated for PFS and used to estimate the PFS-6 along with its 2-sided 90% and 95% CIs. The CIs for PFS-6 will be calculated by applying asymptotic normality to the log-log transformation of PFS-6.

PFS-6 will be compared between the three treatment groups (Arm A, B and C). P-values will be presented without multiplicity adjustment. The comparisons will include the following:

- MEDI4736 + tremelimumab combination therapy (Arm A) versus MEDI4736 monotherapy (Arm B)
- MEDI4736 + tremelimumab combination therapy (Arm A) versus tremelimumab monotherapy (Arm C)

The comparison of PFS-6 will be performed by normal approximation under log-log transformation of Kaplan-Meier estimates of PFS-6 ([Klein et al, 2007](#)).

Specifically, the log HR (1 for combination vs 2 for monotherapy) is estimated as

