$$\log(-\log(\hat{S}_1(t))) - \log(-\log(\hat{S}_2(t)))$$

The variance for log HR is estimated as

$$\frac{Var(\hat{\zeta}_1(t))}{\hat{\zeta}_1(t)(\log(\hat{\zeta}_1(t)))^2} + \frac{Var(\hat{\zeta}_2(t))}{\hat{\zeta}_2(t)(\log(\hat{\zeta}_2(t)))^2}$$

where $\hat{\zeta}(t)$ is the Kaplan-Meier estimate of the progression free survival function, $Var(\hat{\zeta}_i(t)) = \hat{\zeta}_i(t)^2 \sum_{t_{ik} \leq t} \frac{d_{ik}}{n_{ik}(n_{ik}-d_{ik})}$ is the variance for $\hat{S}_i(t)$ derived from Greenwood's formula. d_{ik} and n_{ik} refer to the number of events and number of subjects at risk in the i^{th} group at time t_{ik} , respectively. The final estimate of HR and corresponding 95% CI will be obtained by taking the exponential of log HR and its 95% confidence limits.

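### The 85% power quoted for Arm A versus Arm C is set at 1-sided alpha 0.10; the ORR test the SAP prescribes (Fisher's exact, 2-sided 0.05) has about 57% at the same sizes and rates

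*SAP*

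**What the plan says.** **Planning (SAP 2.4.2, Arms A, B and C).** "Approximately 125 subjects will be randomly assigned in a 2:2:1 ratio to Arms A, B, or C", which is 50, 50 and 25. After a 10% allowance for subjects who are not evaluable or drop out early, the SAP expects about 45 evaluable subjects in each of Arms A and B and about 22 in Arm C. It then says that, for Arm A against Arm C, "the study has 85% power to detect a difference of 35% vs 10% in the response (or PFS-6) rates assuming a 1-sided" alpha of 0.10. It names no test. The same section says that the sample size rests primarily on precision of estimation.

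**Analysis (SAP 3.4.1, ORR).** A versus C is one of two listed comparisons. "P-values for comparisons of ORR between the treatment groups mentioned above will be obtained from" Fisher's exact test. The level follows: "The statistical significant treatment difference will be tested against 2-sided alpha level of 0.05". Also, "P-values will be presented without multiplicity adjustment".

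**Analysis (SAP 3.4.1, PFS-6).** "The comparison of PFS-6 will be performed by normal approximation under log-log transformation of Kaplan-Meier estimates of PFS-6". No significance level is given for this comparison.

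**The concern.** ORR is a co-primary endpoint for Arms A, B, C and E, and A versus C is the only comparison for which the SAP gives a conventional power figure at a stated alpha. The section that gives the figure and the section that defines the test use different alphas and different sidedness, and nothing connects them.

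What is at stake is how a non-significant result is read. Someone who finds a Fisher p-value above 0.05 for A versus C and turns to the sample-size section will see 85%. They may conclude that a 25-point difference has been made unlikely, with a 15% risk of having missed it. For the test actually run, that risk is nearly three times as large.

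**Working it through.** **Inputs**
- Evaluable subjects: n_A = 45, n_C = 22 (SAP 2.4.2).
- True rates: p_A = 0.35, p_C = 0.10 (SAP 2.4.2).
- Planning level: 1-sided 0.10, z = 1.2816 (SAP 2.4.2).
- Analysis: Fisher's exact test, 2-sided 0.05 (SAP 3.4.1).

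**Step 1. Reproduce the SAP figure.** Normal approximation with pooled variance under the null:

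- Pooled rate = (45 × 0.35 + 22 × 0.10) / 67 = 17.95 / 67 = 0.2679.
- SE under the null = √[0.2679 × 0.7321 × (1/45 + 1/22)] = 0.1152.
- SE under the alternative = √[0.35 × 0.65/45 + 0.10 × 0.90/22] = 0.0956.
- Power = Φ[(0.25 − 1.2816 × 0.1152) / 0.0956] = Φ(1.070) = **85.8%**.

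This agrees with the stated 85%.

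**Step 2. Change only the alpha.** With 2-sided 0.05, z = 1.9600:

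- Power = Φ[(0.25 − 1.9600 × 0.1152) / 0.0956] = Φ(0.253) = **60.0%**.

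**Step 3. Use the prescribed test.** Enumerate all 46 × 23 outcomes (x responders in Arm A, y in Arm C). Add the probabilities Bin(x; 45, 0.35) × Bin(y; 22, 0.10) over every outcome with a 2-sided Fisher p-value of 0.05 or less:

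- Power = **56.8%**; chance of missing the difference = 100% − 56.8% = 43.2%.

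**Step 4. Separate alpha from test.**

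| Method, 45 vs 22 | 1-sided 0.10 | 2-sided 0.05 |
|---|---|---|
| Pooled z, normal approximation | 85.8% | 60.0% |
| Pooled z, exact enumeration | 87.5% | 63.9% |
| Fisher's exact, enumeration | 78.0% | 56.8% |

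Changing the alpha costs 21 to 26 points in every row. At 2-sided 0.05, using Fisher's test costs a further 3 points against the approximation (60.0 − 56.8) or 7 points on exact enumeration (63.9 − 56.8).

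**Step 5. Sensitivity of the 56.8%.**
- Arm C rounded up from 22.5 to 23: 58.6%.
- 2-sided p-value taken as twice the 1-sided one (1-sided 0.025): 49.7%.
- Planned As-treated sizes, 50 versus 25, with 35% and 10% holding in all treated subjects: 63.8%. This case matters because "The primary efficacy analyses for the primary efficacy endpoint(s) will be based on the As-treated Population".
- The same 50 versus 25, with the 10% non-evaluable counted as non-responders (0.9 × 35% = 31.5% and 0.9 × 10% = 9%): 56.3%.

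All of these are far below 85%.

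**The case against.** The strongest reply is that nothing here is miscalculated and nothing is hidden. The 85% reproduces, and its alpha is stated in the same sentence. That stands. A reader might infer that the sample-size arithmetic is wrong, and the documents do not support that.

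Second, the figure carries little weight. The arms were sized primarily for precision, the block is headed as preceding Protocol Amendment 6, and Protocol 4.8.3.1 plans only estimates and intervals for the co-primary endpoints. A liberal planning alpha with conventional p-values at reporting is a defensible phase 2 choice. This also stands, and it keeps the point minor. It also means that the finding does not show the arms to be too small for their stated purpose. It does not remove the mismatch: 3.4.1 still prescribes the test at its own level, and the SAP's amendment table shows that 2.4.2 was still being corrected in version 2.1 (2019).

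Third, a reader might carry the same alpha gap over to PFS-6, since the power sentence covers both endpoints and 3.4.1 says "The final estimate of HR and corresponding 95% CI will be obtained by taking the exponential of log HR and its 95% confidence limits". The documents do not support that step. The 2-sided 0.05 sentence sits in the ORR text. The PFS-6 text sets no test level, and a 95% interval is a reporting choice: SAP 3.1 has intervals produced at both 90% and 95%. A large-sample power figure for the log-log comparison would also be fragile. At a true rate of 10% in 22 subjects without censoring, the chance that nobody is progression-free at 6 months is 0.9^22 = 9.8%. The Kaplan-Meier estimate is then 0 and the log-log transform is undefined.

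Finally, it is tempting to say which alpha is the right one. The documents do not show which was intended, so the request is to reconcile them.

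**Conclusion.** The inconsistency holds for ORR and is minor. The stated 85% belongs to a 1-sided 0.10 comparison. The ORR test in SAP 3.4.1 has about 57% power at the same 45 versus 22 and the same 35% versus 10%, a gap of about 28 points (85 − 56.8), most of it due to the alpha.

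The 57% assumes those true rates, the planned evaluable numbers, and rejection when the 2-sided Fisher p-value is 0.05 or less. It is a planned-size figure. Protocol 3.1.1 reports that enrolment into Arms A, B and C was stopped, with 89 subjects in Arms A to D combined at Amendment 6, against about 125 planned for A to C alone. At the same rates the power actually available is therefore lower. It cannot be quantified, because the per-arm counts are redacted.

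For PFS-6, the only conclusion is that 3.4.1 states no test level.

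**What to change.** In SAP 2.4.2, after the A versus C power sentence, reconcile the alpha with 3.4.1. State that the 85% is not the power of the ORR test in 3.4.1, and that Fisher's exact test at 2-sided 0.05 has about 57% power at 45 versus 22 for 35% versus 10%. Note that these are planned sizes and that enrolment into Arms A to C was stopped before the planned 125. In the PFS-6 part of 3.4.1, state the level at which that comparison is to be judged, or say that none applies.

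The cost is two or three sentences. No analysis, endpoint or sample size changes. The only price is a less favourable power figure on the page.

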3 STATISTICAL METHODS

3.1 General Considerations

Categorical data will be summarized by frequency distribution (number and percentage of subjects falling within each category). Continuous variables will be summarized by descriptive statistics including N, mean, standard deviation, median, and range (minimum and maximum). All available data will be used and thus missing data will not be imputed. In general, subjects with missing data for a parameter will be excluded from the summary of this parameter. Tables will be summarized by treatment group. Treatment group refers to dose cohorts in phase 1b and treatment arms in phase 2. Tables will be supported by data listings showing the original data forming the basis for the summaries. All data will be provided in data listings sorted by treatment group, subject number and date collected where applicable.

Two-sided confidence intervals, whenever specified, will be produced at 90% and 95% significance levels.

In general, the baseline is defined as the last non-missing observation collected on or prior to the date of the first dose of study drug(s) for treated subjects unless stated otherwise.

The data analyses will be conducted using the SAS® System (SAS Institute, Inc., Cary, NC, USA) Version 9.3 or above in Unix (Sun OS) environment. All SAS® programs used to generate analytical results will be developed and validated according to MedImmune SAS® programming standards and MedImmune SAS® validation procedures.

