AE = adverse event; BP = blood pressure; CT = computed tomography; D = day; ECG = electrocardiogram; ECOG = Eastern Cooperative Oncology Group; EOI = end of infusion; [REDACTED] LFT = liver function test; [REDACTED] MRI = magnetic resonance imaging; [REDACTED] tic; Q2W = every 2 weeks; Q4W = every 4 weeks; Q12W = every 12 weeks; [REDACTED]; RECIST = Response Evaluation Criteria in Solid Tumors; [REDACTED] SAE = serious adverse event; TSH = thyroid-stimulating hormone; W = week.

Note: On treatment days, evaluations and sample collections should be conducted prior to administration of MEDI4736/tremelimumab unless otherwise indicated. On nontreatment days, all of the pre-treatment assessments will be performed.

- ^a Disease assessments should occur within 7 days prior to dosing.
- ^b If physical examination or safety laboratory tests are performed within 3 days prior to Dose 1, they do not need to be repeated.
- ^c For all treatment arms: Vital signs (temperature, BP, pulse rate, and respiratory rate) will be measured on MEDI4736 and/or tremelimumab treatment days. Vital signs will be measured within 30 minutes prior to the start of tremelimumab and/or MEDI4736 infusion, every 15 minutes (\pm 5 minutes) during tremelimumab and/or MEDI4736 infusion, at EOI of tremelimumab and/or MEDI4736 infusion (\pm 5 minutes), and at 30 and 60 minutes (\pm 5 minutes) post EOI of tremelimumab and/or MEDI4736 infusion. To clarify for subjects receiving combination therapy, vital signs will be measured within 30 minutes prior to start of tremelimumab and MEDI4736 infusion, every 15 minutes (\pm 5 minutes) during tremelimumab and MEDI4736 infusion, at EOI of tremelimumab and MEDI4736 infusion (\pm 5 minutes), and at 30 and 60 minutes (\pm 5 minutes) post EOI of MEDI4736 infusion. For the first day of administration of investigational product, an additional 2-hour (\pm 15 minutes) post EOI period of observation will be required following the 60 minutes (\pm 5 minutes) post EOI assessment of vital signs. For subsequent doses, the additional 2-hour observation period will not be required unless clinically indicated (eg subject experiences an infusion reaction).

^d For all treatment arms: On Day 1 of Week 1, a single ECG will be obtained within 30 minutes prior to start of infusion, within 30 minutes post EOI, and between 2 and 6 hours post EOI of tremelimumab and/or MEDI4736 infusion. To clarify for subjects receiving combination therapy: On Day 1 of Week 1, a

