4.3.4 Medical History, Physical Examination, Electrocardiogram, and Vital Signs

4.3.4.1 Medical History and Physical Examination

Physical examinations will be performed according to institutional guidelines on study days noted in Section 4.2, and will include assessments of the head, eyes, ears, nose, and throat, respiratory, cardiovascular, GI, urogenital, musculoskeletal, neurological, psychiatric, dermatological, hematologic/lymphatic, and endocrine systems; weight; and height (at screening only).

Findings from medical history (obtained at screening) and physical examination shall be given a baseline grade according to the procedure for AEs. Increases in severity of pre-existing conditions during the study will be considered AEs, with resolution occurring when the grade returns to the prestudy grade or below.

4.3.4.2 *Electrocardiograms*

ECGs (12-lead) will be recorded on study days as noted in Section 4.2. At Week 1 Day 1, single ECGs will be obtained within 30 minutes prior to the start of infusion, within 30 minutes post-, and between 2 and 6 hours post-end of infusion of tremelimumab and/or MEDI4736. All other ECGs will be performed once per visit, (prior to investigational product(s) administration if during the treatment period) and as clinically indicated. In case of clinically significant ECG abnormalities, including an ECG that demonstrates a QT corrected using Fridericia's formula (QTcF) value > 500 milliseconds, 2 additional 12-lead ECGs should be obtained over a brief period (eg, 30 minutes) to confirm prolongation.

The same recorder will be used for each subject at each time point, if possible. Date and time settings should be checked at the start of each study day and aligned with an official timekeeper for all machines used in the study.

Skin preparations should be thorough and electrode positions should be according to standard 12-lead ECG placement.

In this study lead V2 will be analyzed and reported as primary. Lead V5 will be analyzed, for all visits, as backup for the individual where analysis in lead V2 is not deemed possible for pre-dose or significant parts of whole visits or whole visits.

The following variables will be reported: heart rate, PR, RR, QRS and QT intervals from the primary lead of the digital 12-lead ECG.

4.3.4.3 *Vital Signs*

Vital signs (temperature, blood pressure [BP], pulse rate [or pulse oximetry at screening], and respiratory rate) will be measured on study days noted in Section 4.2.

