3.8.5 Other Safety Evaluations

3.8.5.1 Vital Signs

Vital signs will be measured on study days noted in Protocol Section 4.2. Descriptive statistics of baseline value, post-baseline value and change from baseline value for heart rate, blood pressure, temperature, and respiratory rate will be provided for each scheduled assessment including the last assessment on-treatment as well as for the maximum and minimum post-baseline on treatment values.

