3.8.5.2 Electrocardiogram

Electrocardiogram parameters (PR, RR, QRS, QT, QT corrected using Fridericia's formula QTcF) will be summarized using descriptive statistics for actual values and for changes from baseline by treatment arm by scheduled time of evaluation including end of treatment visit as well as for the maximum post-baseline values. The QTcF will be considered as the primary correction method to assess subject cardiac safety.

The notable ECG interval values in maximum absolute QTcF intervals (new > 450 milliseconds, new > 480 milliseconds, new > 500 milliseconds) and the maximum absolute uncorrected QT intervals (new > 500 milliseconds) over all post-baseline evaluations, as well as in QTcF maximum changes from baseline (> 30 and > 60 milliseconds) over all post-baseline evaluations will be summarized by treatment. "New" means the category of the QTc abnormality was not present at baseline and became present at least one post-baseline ECG assessment.

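### The SAP sets baseline by calendar date, so, applied as written, subjects assessed to the Day 1 schedule get a post-infusion baseline for ECG and vital signs

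*SAP*

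**What the plan says.** SAP 3.1 (General Considerations) gives one baseline rule for the whole plan: in general, "the baseline is defined as the last non-missing observation collected on or prior to the date of the first dose of study drug(s". It applies "for treated subjects unless stated otherwise".

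Protocol Table 4.2.2-1, footnote d, sets the ECG times on Week 1 Day 1 for all arms: "within 30 minutes prior to start of infusion, within 30 minutes post EOI, and between 2 and 6 hours post EOI". Protocol 4.3.4.2 repeats the same three times. For combination subjects, the pre-dose ECG is timed from the start of tremelimumab and the two later ones from the end of MEDI4736.

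Footnote c of the same table covers vital signs on every treatment day: "Vital signs will be measured within 30 minutes prior to the start of tremelimumab and/or MEDI4736 infusion, every 15 minutes" during the infusion, then at its end and 30 and 60 minutes later.

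SAP 3.8.5.1 plans "Descriptive statistics of baseline value, post-baseline value and change from baseline value for heart rate, blood pressure, temperature, and respiratory rate", together with maximum and minimum post-baseline values. SAP 3.8.5.2 plans changes from baseline, QTcF increases above 30 and 60 ms, maximum post-baseline values, and counts of new QTcF values above 450, 480 and 500 ms. There, new "means the category of the QTc abnormality was not present at baseline" and that the category appeared at one or more post-baseline ECGs.

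**The concern.** A baseline for a safety summary should be an untreated value. A date-only rule is harmless when a measurement is made once on the first dosing day, before the infusion. That is the default for laboratory samples (Protocol 4.2.2). It fails when the measurement is repeated after dosing on the same date, as ECGs and vital signs are here.

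Three kinds of summary are then at risk:

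- **New QTcF categories.** A category that appears after the first infusion and is still present at 2 to 6 hours counts as present at baseline.
- **Changes from baseline.** Every later change is measured from a value taken under treatment.
- **Post-baseline maxima and minima.** The Day 1 post-infusion readings no longer count as post-baseline.

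The first infusion matters in this trial. Protocol 5.4 notes that infusion reactions are commonly seen around first exposure, and 4.5.1.5 bars primary prophylaxis so that a safety signal is not hidden. ECG and vital signs are named in the Phase 1b primary endpoint and in a Phase 2 secondary endpoint.

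**Working it through.** The plan states no figure to reproduce. The check applies the SAP rule to the protocol schedule.

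**Step 1: the rule.** Take all non-missing observations dated on or before the date of first dose. Baseline is the latest of them.

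**Step 2: ECG.** The eligible readings, in time order, are:

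1. screening (Days -28 to -1, one ECG);
2. Day 1, within 30 minutes before infusion;
3. Day 1, within 30 minutes after the end of infusion;
4. Day 1, 2 to 6 hours after the end of infusion.

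The latest is number 4, a treated value.

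**Step 3: vital signs.** The eligible readings are screening, Day 1 pre-dose, every 15 minutes during infusion, end of infusion, 30 minutes after and 60 minutes after. The latest is the 60-minute reading or, if that is missing, the latest non-missing reading that day. The extra 2-hour observation period on the first day is not stated to include a further vital-sign set.

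**Step 4: is there an override?**

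- SAP 3.8.5.1 and 3.8.5.2 use baseline but do not redefine it.
- The note to Table 4.2.2-1 that assessments precede dosing gives way where the table indicates otherwise, and footnotes c and d do so for vital signs and ECGs.
- The rule in SAP 3.8 on repeated or unscheduled tests concerns by-visit summaries. The Day 1 post-infusion readings are scheduled, and that rule does not define baseline.

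**Step 5: which scheduled post-dose ECGs stay post-baseline?** The count covers the initial treatment period plus follow-up (Protocol Tables 4.2.2-1 and 4.2.3-1). The SAP does not define post-baseline, so it is taken here to mean after the baseline observation.

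| Scheduled post-dose ECG | SAP rule as written | Pre-infusion baseline |
|---|---|---|
| Day 1, within 30 min after infusion | precedes baseline | post-baseline |
| Day 1, 2 to 6 h after infusion | is the baseline | post-baseline |
| Week 9 | post-baseline | post-baseline |
| Day 90 after end of treatment | post-baseline | post-baseline |
| Total post-baseline | 2 of 4 | 4 of 4 |

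**Step 6: effect on the change thresholds (illustration).** Let d be QTcF at 2 to 6 hours minus QTcF pre-dose. Then recorded later change = true later change − d. The documents give no value for d, so the figures below are assumptions. For a true later change of +35 ms:

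- d = 5: 35 − 5 = 30
- d = 10: 35 − 10 = 25
- d = 20: 35 − 20 = 15

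None exceeds 30 ms, so the subject would drop out of the > 30 ms count in each case. If d were negative, later changes would be overstated instead.

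**The case against.** **The rule is hedged and the programming plan is not visible.** The rule is worded as general and open to exceptions, and SAP section 1 places table specifications in a separate statistical programming plan that is not supplied. Programmers may already use the nominal pre-dose record. This stands to the extent that nobody can say from the documents how the tables were built. It does not rescue the text. The SAP hands named items to that plan (dose-intensity details in 3.3.3, reduced re-treatment analyses in 3.2) but not baseline. If the programming goes by time, the SAP misdescribes the analysis.

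**The protocol shows a different intent.** Protocol Table 4.2.1-1 labels the Day -28 to -1 assessments, including ECG and vital signs, as screening/baseline. That suggests an untreated baseline was meant, but it does not displace the SAP's explicit rule.

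**Little depends on these summaries.** They are descriptive, and first-infusion problems have other routes into the report. Treatment-emergent adverse events are counted from first receipt of treatment. DLTs and infusion reactions are graded events. A QTcF above 500 ms triggers repeat ECGs. SAP 3.8.5.2 also summarises actual ECG values by scheduled time, and all data are listed. Phase 1b enrolled 6 subjects and is complete. All of this stands and limits the reach of the point.

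**Stronger conclusions that a reader might draw do not hold.**

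- *Every subject has a post-dose baseline.* A subject with no non-missing reading after the start of infusion on Day 1 keeps a pre-dose or screening value.
- *Only one on-treatment ECG visit, Week 9, is left.* SAP 3.8 extends on-treatment to 90 (+7) days after the last dose unless subsequent anticancer therapy starts first, so the Day 90 ECG can qualify. ECGs are also taken when clinically indicated, and the schedule repeats for reinduction, retreatment and crossover.
- *Any change during the first infusion becomes the reference value.* Only what is still present at the last Day 1 reading does.
- *Any QTcF category that emerges on treatment is lost.* One that first appears at Week 9 or later is still new.

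**Conclusion.** The baseline rule in SAP 3.1 is wrong as written for ECG and vital signs. It names a treated value as the reference for subjects assessed to the Week 1 Day 1 schedule, in all arms. For ECGs, 2 of the 4 scheduled post-dose readings in the initial period plus follow-up remain post-baseline, against 4 of 4 with a pre-infusion baseline. For vital signs the loss is confined to the Day 1 readings after the start of infusion, because later treatment days supply many post-baseline values.

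The affected outputs are changes from baseline, new QTcF categories, and post-baseline maxima and minima. No efficacy endpoint, hypothesis test or sample size is touched.

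The conclusion assumes that the rule is applied literally, that the Day 1 readings were taken as scheduled, and that the legible ECG rows of the schedule tables are complete. The size of any shift in QTcF or vital signs cannot be derived from the documents.

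**What to change.** In SAP 3.1, define baseline as the last non-missing value before the start date and time of the first infusion of any study drug. Then add two rules:

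- For Week 1 Day 1 assessments with several time points, use the record nominally labelled pre-dose. If it is missing, use the latest earlier value, such as screening.
- Treat all Day 1 readings taken after the start of infusion as post-baseline in the change, new-category, maximum and minimum summaries.

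The cost is a short edit to the SAP and a time-point filter in the ECG and vital-sign programs. The protocol already schedules the pre-dose readings, so no new data are needed. If the programs already work this way, only the SAP text changes.
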